Patients referred to The Miriam Hospital Kidney Stone Center / Brown Urology for complex kidney stone disease and scheduled for percutaneous nephrolithotomy (PCNL) during the active study enrollment period who meet inclusion criteria will be offered participation in the study. Our center performs approximately 75 PCNLs yearly and we anticipate enrolling 25 patients, which will be adequate to demonstrate the safety and feasibility of the protocol (see Statistical Design and Power).

Urology housestaff and an attending urologist are on call 24 hours a day. Patients will be encouraged to reach out via telephone for questions concerning the study or continued participation. At the postoperative follow up visit (scheduled for 7-10 days after surgery), the research assistant will administer the Ureteral Stent Symptom Score (USSQ), a validated questionnaire regarding postoperative pain control. This will also function to establish continued participation in the study. Patients will complete their participation in the study 30 days after surgery.

Study Timeline:

Two months after notice of award, eligible patients scheduled for percutaneous nephrolithotomy (PCNL) will be offered participation in the study. The study will accrue patients through for one year or until the enrollment goal (25 patients) has been met. Statistical analysis will be performed following accrual and initial findings will

be summarized and reported per protocol to COBRE Opioids and Overdose as well as ClinicalTrials.gov approximately 24 months after notice of award.

Protocol:

Informed consent will be obtained at the time of consent for surgery in the outpatient urologic clinic setting. Either the principal investigator or the trained research assistant (TBA) will conduct the consenting process. Consent will be in written form. A description of the study will be described by the physician or research assistant and will be provided in written form. Patients deemed able to consent for the surgery will have capacity to consent to participation in the study. Patients not able to consent to surgery will not be eligible for the study. The consent process will inform a volunteer about the study, indicate the participation is voluntary and he/she has the right to stop at any time. Risks will be enumerated in the informed consent form and described verbally during the consent process.

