After written consent and enrollment, patients will undergo preoperative counseling regarding pain after PCNL in the preoperative holding area prior to surgery. The patient will then undergo percutaneous nephrolithotomy. No procedural changes will be made for study participants. The procedure will follow standard of care for PCNL. The nonopioid pathway will be discussed with the anesthesia team intraoperatively. Postoperatively, patients will be admitted to the post-anesthesia care unit (PACU) and standard of care adjunctive and analgesic medications will be administered. The patient will be admitted to the floor following surgery and postoperative specialized nonopioid PCNL pathway orders will be communicated to nursing staff via electronic medical record. The patient's pain will be treated with multimodal nonopioid analgesic agents such as cold packs, repositioning, ambulation, acetaminophen, tamsulosin, phenazopyridine, ketorolac, and oxybutynin on an as necessary basis (medications contraindicated due to allergy or intolerance will not be administered). Opioid medications **will not be withheld** for patients with severe (8-10 score on the numerical rating scale) pain. The patient's pain will be recorded by nursing staff every 4 hours as in standard of care. On postoperative day one (POD#1), the patient will be assessed for discharge as in standard of care. They will be asked about their perceived need for a prescription for opioids. If requested, the patient will be given a prescription for a limited quantity of opioids (five [5] tabs of 5mg oxycodone to be taken every 8hours only as necessary for severe 8-10 pain). Nursing staff will complete specialized nonopioid PCNL pathway instructions and patients will be given written instructions regarding medications and activity. Patients will be seen in 7-10 days for stent removal in the office per standard of care, and will complete the Ureteral Stent Symptom Questionnaire (USSQ), a validated quality of life survey for pain after kidney stone surgery.

Specific multimodal interventions of the pathway:

- Preoperative counseling script regarding pain after PCNL surgery
- Post-Anesthesia Care Unit (PACU) nursing instructions and standard recovery medications
- Perioperative pain protocol EMR orderset including medication instructions
- Tailored PCNL discharge instructions for patients and nursing staff
- Standardized discharge medication prescriptions

Primary study outcome:

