- Feasibility of the protocol (number of enrolled patients / patients approached),
- Adherence to and acceptability of the protocol (dropout of enrolled patients and patient satisfaction)

- Adverse events (AEs) while inpatient and following discharge
- Discharge following PCNL without prescription for opioid medications

Secondary study outcomes:

- Postoperative inpatient opioid utilization (morphine mEq / kg / day)
- Opioid prescriptions written at time of discharge (morphine mEq / kg / day)
- Ureteral Stent Symptom Questionnaire (USSQ)¹⁴ scores at postoperative visit
- Non-opioid medications given for pain
- Length of stay (hours)
- Calls to clinic for pain / discomfort within 30 days
- Requests for refills or opioid prescriptions within 30 days
- Presentations to ED for pain within 30 days

Data Analysis:

The protocol will be assessed for feasibility of implementation and safety through analysis of acceptability (number of enrolled patients / patients approached), Adherence to and acceptability of the protocol (dropout of enrolled patients and patient satisfaction via a validated questionnaire (USSQ) and adverse events (AEs) while inpatient and following discharge. Statistical analysis of the pre- and post- intervention groups will be performed to assess for significant overall reduction in opioid prescriptions. Analysis of the patient characteristics and primary / secondary outcomes of the patients will be used to assess potential reasons for opioid necessity following PCNL. A Redcap database designed with assistance from the Data and Research Methods core will be maintained in accordance with the institutional data safety plan.

Statistical Analysis Plan:

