enrolled patients and patient satisfaction via a validated questionnaire (USSQ) and adverse events (AEs) while inpatient and following discharge. Statistical analysis of the pre- and post- intervention groups will be performed to assess for significant overall reduction in opioid prescriptions. Analysis of the patient characteristics and primary / secondary outcomes of the patients will be used to assess potential reasons for opioid necessity following PCNL.

Data Safety Plan:

A minimum of PHI (protected health information) that might identify patient participation will be collected for data analysis purposes. HIPAA identifiers that will be collected include medical record number (MRN) and date of surgery. All HIPAA identifiers will be coded and a de-identified separate database will be held electronically in a secure password protected workstation.

Potential Risks:

Besides the risks of the surgical procedure itself which apply to participants and nonparticipants equally, potential risks of the study include inadequate treatment of pain postoperatively. Patients will be queried prior to discharge on their comfort level regarding discharge without opioid pain medications, and opioids will not be withheld if requested or if the physician feels the patient will not be successfully discharged without opioid prescription. If pain is not controlled after discharge, urology housestaff and an attending urologist are available 24 hours a day for telephone consultation and pain medication refill requests.

This risk is not unique to study participants. Following surgery, there is always a risk of inadequate treatment of pain postoperatively, even with those prescribed opioids. The benefits of avoiding opioids have been well described and potentially outweigh the risks of undertreatment of pain. Additionally, patients exposed to opioids are at risk for opioid induced hyperalgesia. Opioid exposure has been linked to chronic opioid use in patients undergoing ureteroscopy as well, and opioid avoidance can mitigate that risk. Other potential risks including the risks to privacy and/or confidentiality due to data breach will be mitigated with the data safety plan above.

Informed Consent and Assent:

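### Inpatient pain scores bear directly on the study's named risk and are recorded every 4 hours, but no outcome or analysis uses them

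*Combined protocol and SAP*

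**What the plan says.** **Pain recording.** Under Protocol, "pain will be recorded by nursing staff every 4 hours as in standard of care". The preceding sentence names the scale: opioids are not withheld "for patients with severe (8-10 score on the numerical rating scale) pain".

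**The risk.** Under Potential Risks, "potential risks of the study include inadequate treatment of pain postoperatively". The same section adds, in the context of discharge, that "opioids will not be withheld if requested or if the physician feels the patient will not be successfully discharged without opioid prescription".

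**The outcomes.** The primary list has enrolment relative to patients approached, dropout and satisfaction, adverse events, and opioid-free discharge. The secondary list has inpatient and discharge opioid amounts, USSQ scores, non-opioid medications, length of stay, and calls, refill requests and emergency visits to 30 days. The USSQ, described as "a validated questionnaire regarding postoperative pain control", is given 7 to 10 days after surgery.

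**The analyses.** Data Analysis and the Statistical Analysis Plan cover feasibility, acceptability, adverse events, a before/after comparison of opioid prescriptions, and an exploration of why patients needed opioids. That exploration is confined to patient characteristics and the listed outcomes.

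**Sample size.** Study Design and the Statistical Analysis Plan give 15 + 15 = 30 patients. Inclusion of Women and Minorities, Recruitment and retention plan, and Study Timeline give 25. The recruitment section says that 25 will be enough to show safety and feasibility.

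**The concern.** The hypothesis in the Background is that the pathway cuts opioid prescriptions without affecting clinical outcomes. The stated long-term goal is a randomised trial of pain control. The clinical outcome most directly exposed is pain during the stay, when the pathway replaces routine opioids with other measures. That pain is charted in routine care but is not planned to be reported.

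What is at stake is the reading of a listed secondary outcome. If inpatient opioid use falls, patients may have needed less, or may have had the same pain with less treatment. The plan has no inpatient pain measure to set beside the fall. If the scores are examined later without a prespecified summary and window, the choice of mean, maximum or time span will be made after the data are seen.

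**Working it through.** **1. Does anything already listed measure inpatient pain?**

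| Candidate | Why it does not fill the gap |
|---|---|
| USSQ | Given at 7–10 days, after the stay |
| Calls, refill requests, emergency visits | Cover pain after discharge |
| Inpatient opioid use | The pathway is designed to lower it |
| Non-opioid medications | Indirect, and part of the pathway itself |
| Inpatient adverse events | Rely on reports by nurses and physicians; no pain score or threshold is defined as an event |
| Opioid access at scores of 8–10, or on request at discharge | Limits under-treatment but does not measure it |

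None does. Because the recording is standard of care, the scores should exist for both cohorts.

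**2. How many readings would there be?** Study Design describes such procedures as having less than 24 hours of observation. At one reading every 4 hours, 24 / 4 = 6 is about the most to expect in a typical stay. Counting from arrival on the floor, after recovery-unit time, gives fewer. A 24-hour window would often end at discharge, and length of stay is itself an outcome, so the averaging period could differ between cohorts. A shorter window avoids this. For illustration, 12 hours would hold about 12 / 4 = 3 readings.

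**3. What precision would the new outcome have?** Input: 15 per cohort (Statistical Analysis Plan). The 95% CI half-width for a difference in means is t(0.975, 28) × √(2/15) × SD = 2.048 × 0.365 × SD = 0.748 SD. The documents give no SD. Assuming 2.0 to 2.5 points on the 0–10 scale:
- SD 2.0: 0.748 × 2.0 = 1.50 points
- SD 2.5: 0.748 × 2.5 = 1.87 points

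**4. What can the sample say about safety?** The only sample-size calculation concerns discharge prescriptions falling from 80% to 50%, so the plan has no safety figure to reproduce. With zero events among n patients, the exact two-sided 95% upper limit is 1 − 0.025^(1/n).

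| Patients on the pathway | Basis | Upper limit |
|---|---|---|
| 15 | 30 in total, as in Study Design | 21.8% |
| 13 | 25 in total, split over two cohorts | 24.7% |
| 12 | 25 in total, split over two cohorts | 26.5% |
| 25 | only if all 25 were on the pathway | 13.7% |

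**The case against.** The strongest reply is that this is a small feasibility pilot with four primary and eight secondary outcomes. A ninth would exclude only large differences, and no conclusion about prescriptions, dropout or enrolment would change. That is fair, and it limits the weight of the point. It does not defeat an outcome offered for estimation only, because the existing secondary outcomes face the same sample size.

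A second reply is that inpatient adverse events are already a primary outcome and are compared with standard care. This is the nearest existing route for under-treated pain. Without a pain criterion, however, it depends on someone choosing to report pain as an event.

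A third is that the scores are themselves exposed to the pathway. This stands in part. On the pathway, "patients will undergo preoperative counseling regarding pain after PCNL", which may shift how pain is reported. The range 8–10 is also the level at which the pathway says opioids are not withheld, so scores there may be given or recorded differently after implementation. The mean score is therefore the better main summary, and any 8–10 score should be descriptive only.

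It is tempting to add that the pilot would supply the SD for the randomised trial. That benefit is weak. From 15 patients, the 95% limits are √(14/χ²), or 0.73 to 1.58 times the estimate. The 64 patients from 2018 could give a larger standard-care sample if their scores can be retrieved.

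A reader might also infer that the study ignores pain, or that pathway patients are left without relief. The documents support neither: pain after discharge is followed to 30 days and opioid access is preserved.

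**Conclusion.** The omission is clear from the text. Inpatient pain intensity is charted, bears on the study's named risk, and enters no outcome or analysis. As planned, a fall in inpatient opioid use cannot be told apart from under-treated pain. Reporting the score narrows that ambiguity but does not remove it, because the cohorts are small and unrandomised. At 15 per cohort the comparison would have a half-width of about 0.75 SD; the figure in points rests on an assumed SD. It could not support a claim that pain was no worse.

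This is a cheap improvement that should be made. It does not invalidate the prescription analysis.

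The safety wording is a separate, smaller matter and adds no weight to the pain point. No calculation supports it at any of the possible sizes. A reader might take the conflict to be 15 versus 25 patients on the pathway. The text better supports a total of 30 versus a total of 25, with the pathway number following from whichever is meant. The 13.7% limit should therefore not be relied on.

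**What to change.** **Pain outcome.** Add one secondary outcome in both cohorts: the mean inpatient pain score per patient over a common early window from floor arrival. Fix the window in advance, shorter than 24 hours, so that nearly all patients complete it. Then:
- report the number of readings per patient;
- give the between-cohort difference with a 95% CI beside inpatient opioid use;
- label it as estimation from an unrandomised before/after comparison;
- if any score of 8–10 is shown, keep it descriptive, with the caveat that counselling and the pathway's use of that range may change how scores are reported.

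**Safety wording.** In Recruitment and retention plan, change the stated purpose from *demonstrating* to *estimating* safety and feasibility. Report adverse events per cohort with exact 95% CIs. Reconcile total enrolment (30 or 25) throughout and state the resulting number on the pathway.

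**Cost.** Extraction of time-stamped scores for about 30 patients and a few sentences of analysis plan, with no new patient assessments. The safety claim becomes more modest, and the pain comparison will exclude only large differences.

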Describe what adverse events occur to those on the nonopioid protocol as compared to the standard of care.

Measures: All adverse events occurring as an inpatient will be measured by nursing and physician reporting, and as an outpatient via patient self-reporting, electronic medical records of emergency department visits, requests for opioid prescription refills and telephone calls to clinic.

Begin to reduce overall opioid prescription writing for patients undergoing PCNL at the Miriam Hospital.

Measures: The electronic medical records will be queried for prescriptions written at discharge. The Rhode Island Opioid Prescription Monitoring Program (PMP) will be queried for a 30-day period following surgery to evaluate for opioid prescriptions written by other providers.

Our long-term goal is to determine if this nonopioid recovery pathway for PCNL is more effective for postoperative pain control than the standard of care (routine opioid prescription) and this study will provide the pilot feasibility data to enable a randomized controlled trial (RCT) to be performed.

We have previously demonstrated that outpatient ureteroscopy and stent placement without postoperative opioid prescriptions is possible in the vast majority of patients.⁸ The success of this is dependent upon a multimodal

approach to the patient's experience of undergoing endoscopic kidney stone surgery (ureteroscopy) and focuses on the preoperative, perioperative, and postoperative stages of intervention.⁹

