This is a pragmatic pilot study which will prospectively compare a cohort of 15 patients undergoing PCNL prior to implementation of the novel nonopioid pathway to 15 patients undergoing the same procedure utilizing the novel nonopioid pathway. A historical cohort of patients was analyzed to determine the study population size needed to achieve our goals. Sixty-four patients underwent PCNL at The Miriam Hospital in 2018 and approximately 80% of patients were discharged home with a prescription for opioid pain medication (20% opioid-free discharge rate). Current standard of care following PCNL remains the routine prescription of opioid medications for pain control. Since PCNL is a more invasive procedure than ureteroscopy and is a non-natural orifice surgery, we expect to reduce opioid prescriptions from 80% to 50% (50% opioid-free discharge rate). To power a study with a beta of 0.8 and an alpha of 0.05 requires only a small sample size of 13 patients with this large reduction. In order to account for patient drop out and protocol non-adherence, we plan to enroll 30 patients in our pilot study.

The subject population will be adult patients referred to The Miriam Hospital Kidney Stone Center (Lifespan – Providence, RI) and Brown Urology (Brown Physicians, Inc. – Providence, RI) for complex kidney stone disease and scheduled for percutaneous nephrolithotomy (PCNL) during the active study enrollment period who meet inclusion criteria. As the prevalence of nephrolithiasis in the United States is seen more in men (1.4:1 male vs female),¹³ we anticipate our patient population to include more men than women. The risk difference between men and women, however, has been narrowing and we would expect that given our anticipated study population size of 30 patients, approximately 12-15 patients will be women. Nephrolithiasis affects all races and given the diverse population of the greater Providence, RI region, we anticipate a significant portion of our study population to be of non-white race. Every effort will be made to offer participation to eligible women and minorities.

The protocol will be assessed for feasibility of implementation and safety through analysis of acceptability (number of enrolled patients / patients approached), adherence to and acceptability of the protocol (dropout of

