Informed consent will be obtained at the time of consent for surgery in the outpatient urologic clinic setting. Either the principal investigator or the trained research assistant (TBA) will conduct the consenting process. Consent will be in written form. A description of the study will be described by the physician or research assistant and will be provided in written form. Patients deemed able to consent for the surgery will have capacity to consent to participation in the study. Patients not able to consent to surgery will not be eligible for the study. The consent process informs a volunteer about the study, indicates the participation is voluntary and he/she has the right to stop at any time. Risks are enumerated in the informed consent form and described verbally during the consent process.

Potential Benefits of the Proposed Research to Research Participants and Others:

There is a growing body of literature describing the benefits of opioid avoidance after surgery and the use of adjunct or multimodal nonopioid analgesic agents. Patients participating in the study will benefit from increased surveillance of the adequacy of pain control postoperatively while admitted, and increased availability of staff to address concerns while at home. The risk of opioid hyperalgesia and the potential for opioid tolerance or dependence will be mitigated if participants are not exposed to opioids. The families or cohabitants of the patient will benefit from the lack of opioid medications at home that may be subject to possible diversion or accidental ingestion. In light of these potential benefits, the risks of inadequate pain control are reasonable in relation to the anticipated benefits to research participants.

In light of the opioid epidemic, research that advances our understanding of nonopioid therapies for acute pain after surgery are paramount. This study proposes to evaluate a novel nonopioid pathway for pain control after PCNL, and aims to reduce the opioids administered and prescribed after a common urologic procedure. The

knowledge that will be gained will better inform our practices as urologists and physicians and will allow us to better understand patient characteristics that increase the likelihood of needing opioids after surgery. As such, the risks described above are reasonable in relation to the importance of the knowledge that we will gain from this study.

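### The discharge opioid amount is given per kg per day with 'day' undefined; on its natural readings it does not register how many tablets are prescribed

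*Combined protocol and SAP*

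**What the plan says.** Under Secondary study outcomes, the amount prescribed at discharge appears only as "Opioid prescriptions written at time of discharge (morphine mEq / kg / day". The line above it gives inpatient opioid use in the same unit. Neither Data Analysis nor the Statistical Analysis Plan defines the day, states how patients without a prescription are scored, or names a test.

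Under Protocol, a pathway patient who asks for opioids receives a "limited quantity of opioids (five [5] tabs of 5mg oxycodone to be taken every 8hours only as necessary". The number of tablets is thus part of the intervention.

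The only other discharge-prescription outcome is a yes/no one, opioid-free discharge, listed under Primary study outcome. The third specific aim is to "Begin to reduce overall opioid prescription writing for patients undergoing PCNL", and its measures say that "The electronic medical records will be queried for prescriptions written at discharge". The section on potential benefits says that the study "aims to reduce the opioids administered and prescribed after a common urologic procedure".

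For the control cohort, the Statistical Analysis Plan says only: "Current standard of care following PCNL remains the routine prescription of opioid medications for pain control". No strength, interval or tablet count is given.

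**The concern.** A daily rate suits inpatient use, where drug is given over a stay of measured length. An as-needed take-home prescription has no such length, so the analyst must supply one. The two obvious choices are the maximum daily dose and the days' supply, and both remove the tablet count from the result. The one listed outcome that could describe how much is prescribed would then be blind to a feature that the pathway deliberately changes. Its answer would instead turn on the dosing interval of the control prescriptions, which is undocumented.

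Dividing by weight is a smaller problem of the same kind. The pathway prescription is a fixed quantity, so weight adds variation unrelated to prescribing.

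The primary outcomes are not touched. At stake is the interpretation of one secondary outcome in a pilot meant to prepare a randomised trial, to which an unclear endpoint could carry over.

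**Working it through.** The plan gives no sample size, power or expected value for this outcome, so there is no stated figure to reproduce.

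**Inputs from the documents.** Pathway prescription: 5 tablets of 5 mg every 8 hours as needed, so at most 24/8 = 3 tablets a day, lasting 5/3 = 1.67 days at maximum use. Proportion prescribed opioids: 80% before and 50% on the pathway. Cohorts: 15 and 15.

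**Assumptions.** Conversion of 1.5 morphine mEq per mg (ratios do not depend on it); 5 mg tablets in both cohorts; every pathway prescription is 5 tablets; patients without a prescription count as 0. The control tablet count k and control maximum tablets per day t are varied, because the documents give neither.

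**Step 1: dependence on tablet count.** Let c be the conversion factor.
- Daily dose = t × strength × c. No k appears.
- Total / days' supply = (k × strength × c) / (k/t) = t × strength × c. The k cancels.
- Total / fixed window of W days = k × strength × c / W. This tracks k.

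At 5 mg every 8 hours:

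| Tablets | Total mEq | Per day, maximum use | Per day, days' supply rounded up |
|---|---|---|---|
| 5 | 37.5 | 22.5 | 37.5/2 = 18.75 |
| 10 | 75 | 22.5 | 75/4 = 18.75 |
| 20 | 150 | 22.5 | 150/7 = 21.4 |
| 30 | 225 | 22.5 | 225/10 = 22.5 |

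The total rises 6-fold. The daily figure is constant, or moves between 18.75 and 22.5 through rounding alone.

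**Step 2: effect on the comparison of cohort means.**
- Fall in mean daily dose = 1 − (0.5 × 3)/(0.8 × t): 6% at t = 2, 37.5% at 3, 53% at 4, 69% at 6.
- Fall in mean total = 1 − (0.5 × 5)/(0.8 × k): 37.5% at k = 5, 69% at 10, 84% at 20, 90% at 30.

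The two falls agree when k/t = 5/3 = 1.67 days. The daily dose understates the fall in total when control prescriptions last longer than that at maximum use, and overstates it when they last less (k = 5, t = 4: 53% against 37.5%).

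**Step 3: can it point the wrong way?** Suppose control prescriptions are 20 tablets at up to 2 a day.
- Among recipients, daily dose is 22.5 on the pathway against 2 × 5 × 1.5 = 15 in controls, which is 50% higher. Total is 37.5 against 150, which is 75% lower.
- Over all patients, mean daily dose falls by 6% and mean total by 84%. Below t = 1.5/0.8 = 1.875 tablets a day, the mean daily dose would rise.
- A two-sided 5% rank-sum test (assumed) with tie correction, enumerated over Bin(15, 0.8) and Bin(15, 0.5), is significant on daily dose in 13.7% of trials: 11.5% with the pathway higher and 2.2% with it lower.

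**Step 4: weight.** At illustrative weights of 60 and 100 kg, the same prescription scores 22.5/60 = 0.375 and 22.5/100 = 0.225 per kg per day.

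**The case against.** **The defect depends on the reading.** This stands. What the text establishes is an undefined denominator. A fixed window would track quantity, so the outcome is not blind to quantity on every reading.

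**The yes/no primary already serves the aims.** This largely stands. The 80% to 50% goal and the third aim concern whether prescriptions are written. A reader might infer from the benefits section that tablet quantity at home is a stated concern, but the text is that families "benefit from the lack of opioid medications at home that may be subject to possible diversion or accidental ingestion". That describes absence, which opioid-free discharge measures directly. Only the phrase about reducing opioids administered and prescribed could imply amount, and no section makes showing the effect of the five-tablet limit an objective.

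**The spread across readings exaggerates the harm.** This stands. One pathway prescription is 22.5 mEq per day at maximum use and 37.5/30 = 1.25 over 30 days, and a reader might infer an 18-fold error. A fixed window is one constant applied to both cohorts, so it cancels from the ratio, the percentage fall and any rank test. The contrast that matters is daily dose or days' supply against total or a fixed window.

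**A total would look more powerful only because of the cap.** This stands. By the same enumeration, power on the total is 37% if control prescriptions are also 5 tablets and 96% if all exceed 5. In the latter case every control recipient outranks every pathway recipient, because the protocol fixes the pathway quantity. Unweighted daily dose also reaches 96% at t = 4 or 6. The case for the total is that it measures amount, not that it gains power.

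**The total may be recoverable at analysis.** Probably so, since discharge prescriptions are to be queried. That lowers the severity, but the choice is better made before the data are seen.

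**Conclusion.** The point holds as a minor one. The unit is borrowed from the inpatient outcome and its day is undefined. On its natural readings it is constant, or nearly so, from 5 to 30 tablets while the total differs 6-fold, and no other listed outcome records quantity. That result needs only equal strength and interval.

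The percentage falls and the wrong-direction example rest on the assumed control regimens, the assumed test and zero scores for patients without a prescription. They show what could happen, not what will. A reader might infer that this trial's result will be biased in a known direction. The documents do not support that, because the control regimen is not given and the daily dose can understate, match or overstate the fall in total. The primary opioid-free discharge outcome is unaffected.

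**What to change.** Define the discharge outcome as total morphine equivalents prescribed per patient: tablets × strength × a stated conversion, 0 if none, not divided by weight or day. Report the mean in each cohort and the difference with a 95% confidence interval (for example bootstrap). Beside it, report the proportion prescribed, which is already primary, and the amount among recipients (median and range). A daily rate can stay as a supplementary measure if the day is defined. The inpatient outcome keeps its unit.

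The cost is SAP wording. Discharge prescriptions are already to be queried from the electronic record, and the total needs only tablet count and strength from each.

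The downside is that part of any difference in total follows from the pathway's own quantity limit. If control prescriptions were 20 tablets, the 84% fall would combine 37.5% fewer prescriptions (0.5/0.8 = 0.625) with 75% less per prescription (5/20 = 0.25): 1 − 0.625 × 0.25 = 0.844. The report should describe that share as built in by design and should not present it as a gain in power.
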